## 11.5. Appendix 5: Derived and Transformed Data

### 11.5.1. General

Multiple Measurements at One Time Point

 
Mean of the measurements will be calculated and used in any derivation of summary statistics but if listed, all data will be presented.
 
If there are two values within a time window the value closest to the target day for that window will be used. If values are the same distance from the target then the mean will be taken.
 
Subjects having both High and Low values for Normal Ranges at any post-baseline visits for safety parameters will be counted in both the High and Low categories of “Any visit post-baseline” row of related summary tables. This will also be applicable to relevant Potential Clinical Importance summary tables.
 

Study Day

 
Calculated as the number of days from randomization date : 
 
Ref Date = Missing → Study Day = Missing
 
Ref Date < Randomisation Date → Study Day = Ref Date – Randomisation Date
 
Ref Date ≥ Randomisation Date → Study Day = Ref Date – (Randomisation Date) + 1
 
 
 

### 11.5.2. Study Population

Demographics
Age

 
GSK standard IDSL algorithms will be used for calculating age where birth date will be imputed as follows: 
 
Any subject with a missing date and month will have this imputed as ‘30th June’.
 
Birth date will be presented in listings as ‘YYYY’.
 
Age will be calculated based on date of Screening visit as an Age reference date for Screen failed subjects and based on date of the initial dose date for ITT population.
 
 
 

Age Group

 
The following category will be used for Summary of Demography. 
 
Age ≤ 18 (years)
 
19 < Age < 64
 
65 ≤ Age
 
 
 

Age Category

 
The following category will be used for Summary of Age Ranges. 
 
Age < 18 (years)
 
18 ≤ Age ≤ 64
 
65 ≤ Age ≤ 84
 
85 ≤ Age
 
 
 

Body Mass Index (BMI)

 
Calculated as Weight (kg) / [Height (m)]
 

Demographics																
RA disease history																
RA Disease Duration																

 
RA disease duration will be calculated based on the formula:  <math display="block">\text{Disease Duration in Months} = [\text{Treatment Start Date} - (\text{RA Diagnosis Date})] / 30.25</math> 
rounded to four decimals
 <math display="block">\text{Disease Duration in Years} = [\text{Treatment Start Date} - (\text{RA Diagnosis Date})] / 365.25</math> 
rounded to four decimals
 
 
																
Time since start of RA symptoms																

 
Time since start of RA symptoms will be calculated based on the formula:  <math display="block">\text{Time since start of RA symptoms in Months} = [\text{Treatment Start Date} - (\text{Date of first symptom})] / 30.25</math> 
rounded to four decimals
 
 
																
Prior and Concomitant Medications																
Oral Corticosteroid																

 
To assess corticosteroid use and determine average daily corticosteroid dose, all corticosteroid dosages will be converted to a prednisolone equivalent in milligrams by multiplying the dose of the steroid (using the coded term from GSKDrug) by the conversion factor to get prednisolone equivalent units.
 
The following table will provide the conversion factors.
 
For each scheduled visit, the average daily prednisolone dose will be calculated by summing all prednisolone doses since the previous visit up to and including the current visit and then dividing by the number of days in this period (Date of current visit – Date of previous scheduled visit).
 
If frequency that a subject takes the steroid is less than once daily such as QOD, the dosage will be converted to daily dose and then the average daily dose will be calculated. For example, if a subject takes 10 mg of the steroid QOD, the daily dose is 5 mg/day.
 
																

  
 Conversion	Steroid	
   
 8.333	BETAMETHASONE	
 
 0.2	CORTISONE	
 
 6.667	DEXAMETHASONE	
 
 0.25	HYDROCORTISONE	
 
 1.25	METHYLPREDNISOLONE	
 
 1	PREDNISOLONE	
 
 1.25	TRIAMCINOLONE	
  
	Conversion	Steroid	8.333	BETAMETHASONE	0.2	CORTISONE	6.667	DEXAMETHASONE	0.25	HYDROCORTISONE	1.25	METHYLPREDNISOLONE	1	PREDNISOLONE	1.25	TRIAMCINOLONE
Conversion	Steroid															
8.333	BETAMETHASONE															
0.2	CORTISONE															
6.667	DEXAMETHASONE															
0.25	HYDROCORTISONE															
1.25	METHYLPREDNISOLONE															
1	PREDNISOLONE															
1.25	TRIAMCINOLONE															
Rheumatoid factor (RF)																

 
A subject who has a value of RF <math>> 15</math> IU/mL is positive.
 
Otherwise negative.
 
																
Anti-cyclic Citrullinated Protein Antibody (ACPA)																

 
A subject who has a value of ACPA <math>\geq 4.5</math> U/mL is positive.
 
Otherwise negative.
 
																

Extent of Exposure																	
GSK3196165																	

 
Number of days of exposure to study drug will be calculated based on the formula: Duration of Exposure in Days = Treatment Stop Date – (Treatment Start Date) + 1
 
Subjects who were randomized but did not report a treatment start date will be categorised as having zero days of exposure.
 
The cumulative dose will be based on the formula: Cumulative Dose = Sum of (Actual Volume x One Dosage / Expected Volume)
 
																	

 
The following table provides the one dosage and the expected volume in each dose group.
 
																	

  
 Dose group	One Dosage (mg)	Expected volume (mL)	
   
 Placebo	0	0.6	
 
 45 mg	45	0.3	
 
 90 mg	90	0.6	
 
 180 mg	180	1.2	
  
			Dose group	One Dosage (mg)	Expected volume (mL)	Placebo	0	0.6	45 mg	45	0.3	90 mg	90	0.6	180 mg	180	1.2
Dose group	One Dosage (mg)	Expected volume (mL)															
Placebo	0	0.6															
45 mg	45	0.3															
90 mg	90	0.6															
180 mg	180	1.2															
Methotrexate (MTX)																	

 
Overall Average Weekly MTX dose will be averaged across Week 1 - 12 for each subject based on the formula: Overall Average Weekly MTX Dose = Mean of the Weekly Dosage of MTX
 
																	

### 11.5.3. Safety

Adverse events of special interest will be derived using Common Terminology Criteria for Adverse Events, 2009 v4.0 (CTCAE).

Adverse Events of Special Interest	
Adverse Events of Special Interest are defined as the AEs below. AESI will be specified by Safety Review Team and Japan EST.	

 
Serious infections, including serious respiratory infections and TB.
 
Opportunistic infections
 
Neutropenia
 
Respiratory events as AESI
 
Pulmonary alveolar proteinosis
 
Hypersensitivity reactions, including anaphylaxis
 
Injection site reactions
 
	

Respiratory events	
Events	Definition
Persistent cough with Grade 2 or greater recorded	Cough grade 2 or greater recorded for 3 consecutive weeks (15 or more days) on the eCRF page.
Persistent dyspnea with Grade 3 or greater recorded	Borg Scale grade 3 or greater recorded for 3 consecutive weeks (15 or more days) on the eCRF page.

Respiratory events	
Events	Definition
Persistent decrease of $D_{LCO}$ by > 15%	
Relative decrease of <math>D_{LCO}</math> of >15% compared to baseline for 3 consecutive weeks (15 or more days)
 
Decrease of <math>D_{LCO}</math> = (%change from baseline in <math>D_{LCO}</math>) <math>\times -1</math>
 
A subject's baseline <math>D_{LCO}</math> value will be taken as the lowest value obtained from the Screening assessment or any unscheduled visit in between Screening and Day 1 visit.

Final adjudication will be conducted by the SRT.	

Laboratory Parameters	

 
If a laboratory value which is expected to have a numeric value for summary purposes, has a non-detectable level reported in the database, where the numeric value is missing, but typically a character value starting with '<x' or '>x' (or indicated as less than x or greater than x in the comment field) is present, the number of significant digits in the observed values will be used to determine how much to add or subtract in order to impute the corresponding numeric value. 
 
Example 1: 2 Significant Digits = '< x' becomes <math>x - 0.01</math>
 
Example 2: 1 Significant Digit = '> x' becomes <math>x + 0.1</math>
 
Example 3: 0 Significant Digits = '< x' becomes <math>x - 1</math>
 
 
 
	

#### 11.5.4. Efficacy

ACR 20/50/70 response [American Collenge of Rheumatology Committee to Reevaluate Improvement Criteria, 2007]
Procedure

• The following 7 ACR-core set measures will define ACR20/50/70 response.

• Tender/Painful Joint Count 68 (TJC68)

• Swollen Joint Count 66 (SJC66)

• Patient's Assessment of Arthritis Pain at this time

• Patient's Global Assessment of Arthritis

• Physician's Global Assessment of Arthritis

• C-reactive protein (CRP) (in mg/L)

• Health Assessment Questionnaire-Disability Index (HAQ-DI)

• The %Change from Baseline in each ACR-core set measure will be calculated.

• If %Change from Baseline in both tender and swollen joint counts are less than -20% and those in 3 of the 5 remaining ACR-core set measures are less than -20%, ARC20 criteria is met.

• Similarly ACR50 and 70 are calculated with the respective percent improvement.

• For all visits if any of the component scores are missing, then those scores will considered as not having met the criteria for improvement. Therefore, if TJC68 or SJC66 or 3 or more of the 5 remaining ACR-core set measures are missing, ACR20/ ACR50/ ACR70 will each be considered as "no response"

• For component scores with missing Baseline values or a Baseline value of 0, the percentage improvement cannot be calculated and the component will be considered as not having met the criteria for improvement for all visits.

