7.6.6. ACR Assessments

The American College of Rheumatology's definition for calculating improvement in RA (ACR20) is calculated as a 20% improvement in tender and swollen joint counts and 20% improvement in 3 of the 5 remaining ACR-core set measures: patient and physician global assessments, pain, disability, and an acute-phase reactant. Similarly, ACR50 and 70 are calculated with the respective percent improvement. This efficacy measurement will be made at every study assessment timepoint.

The specific components of the ACR Assessments that will be used in this study are:

- Tender/Painful Joint count (68).
- Swollen Joint Count (66).
- Patient's Assessment of Arthritis Pain.
- Patient's Global Assessment of Arthritis.
- Physician's Global Assessment of Arthritis.
- CRP or ESR.
- Health Assessment Questionnaire – Disability Index (HAQ-DI).

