6. CRP
7. Health Assessment Questionnaire-Disability Index (HAQ-DI)

%changes from baseline in **tender and swollen joint count**  $\leq -X$

Yes

No

The subject did not meet the criteria for ACRX

%changes from baseline in 3 of the **5 remaining components**  $\leq -X$

Yes

No

The subject did not meet the criteria for ACRX

The subject met the criteria for ACRX

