**Examples**

- The subject did not met the criteria for ACR20

Component	Baseline	Post-dose visit value	%change
TJC68	43	14	-67
SJC66	38	44	16
Patient's Assessment of Arthritis Pain	46	20	-57
Patient's Global Assessment of Arthritis	85	31	-64
Physician's Global Assessment of Arthritis	75	27	-64
CRP	2.8	2.0	-29
HAQ-DI	11.6	7.2	-38

- The subject met the criteria for ACR50 but not ACR70

Component	Baseline	Post-dose visit value	%change
TJC68	43	14	-67
SJC66	38	14	-63
Patient's Assessment of Arthritis Pain	46	10	-78
Patient's Global Assessment of Arthritis	85	31	-64
Physician's Global Assessment of Arthritis	75	27	-64
CRP	2.8	1.0	-64
HAQ-DI	11.6	1.2	-90

**Disease Activity Score**[Prevoo, 1995; Fransen, 2005; Wells, 2009]

- The DAS assessment is a derived measurement with differential weighting given to each component. The DAS28 (CRP) and DAS28 (ESR) will be calculated at each assessment time point.
- The components of the DAS28 arthritis assessment include:
  - Tender Joint Count 28 (TJC28)
  - Swollen Joint Count 28 (SJC28)
  - C-reactive protein (CRP) (in mg/L) or Erythrocyte sedimentation rate (ESR) (in mm/hr)
  - Patient's Global Assessment of Arthritis (PtGA) (visual analogue scale with values from 0 = best to 100 = worst)

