### Health Assessment Questionnaire-Disability Index (HAQ-DI)[Fries, 1980; Matsuda, 2003]

#### Procedure

[figure not shown]
- The functional status of the subject will be assessed by means of the Disability Index of the Health Assessment Questionnaire. This 20-question instrument assesses the degree of difficulty a person has in accomplishing tasks in eight functional areas:
  - Dressing & grooming
  - Arising
  - Eating
  - Walking
  - Hygiene

- Reach
- Grip
- Activities
- Each functional area contains at least two questions. For each question, there is a four level response set that is scored from 0 (without any difficulty) to 3 (unable to do). If aids or devices or physical assistance are used for a specific functional area and the maximum response of this functional area is 0 or 1, the according value is increased to a score of 2.

Aid or device	Functional area
Devices used for dressing	Dressing and grooming
Special or built up chair	Arising
Built up or special utensils	Eating
Cane	Walking
Crutches	Walking
Walker	Walking
Wheelchair	Walking
Bathtub seat	Hygiene
Bathtub bar	Hygiene
Raised toilet seat	Hygiene
Long-handled appliances in bathroom	Hygiene
Long-handled appliances for reach	Reach
Jar opener	Grip

- Regarding these corrections, the highest response within each functional area determines the score of that specific functional area. If no questions within a given functional area were answered, no score will be provided for that category (even if answers on aids or equipment are available).
- HAQ-DI is only calculated if there are at least 6 functional area scores available.
- The average of these non-missing functional area scores defines the continuous HAQ-DI score ranging from 0 to 3. If there are less than 6 functional area scores available, no imputation will be done and the HAQ-DI will be set to missing for the according assessment.

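### SAP 11.5.4 gives two cutoffs for ACR20: strictly below -20% in the procedure text, at or below -X in the flowchart; the sign for ACR50 and ACR70 is left unclear (exploratory endpoints)

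*SAP*

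**What the plan says.** The ACR procedure in SAP 11.5.4 defines ACR20 in words. For the joint counts: "If %Change from Baseline in both tender and swollen joint counts are less than -20"%. For the rest: "those in 3 of the 5 remaining ACR-core set measures are less than -20%, ARC20 criteria is met". The next bullet covers the other two levels: "Similarly ACR50 and 70 are calculated with the respective percent improvement".

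The flowchart that follows in the same section is written for a general level X. Its first step is "changes from baseline in tender and swollen joint count $\leq -X" and its second is "changes from baseline in 3 of the 5 remaining components $\leq -X".

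Two worked examples come next. In one the subject fails ACR20. The other is labelled "The subject met the criteria for ACR50 but not ACR70".

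Protocol 7.6.6 says that ACR20 "is calculated as a 20% improvement in tender and swollen joint counts", with the same percentage for 3 of the 5 other measures. It gives no inequality sign.

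SAP 11.4.2.2 defines percent change as 100 × (post-dose − baseline) / baseline, so improvement is negative. ACR20/50/70 response rates are exploratory endpoints (SAP 2.2).

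**The concern.** Two rules in one section treat a change of exactly -20% in opposite ways. Two programmers who each follow SAP 11.5.4 faithfully can produce different ACR20 tables and bar plots (Tables 2.5 to 2.7 and Figures 2.6 to 2.8 hold the three ACR levels). The difference from placebo and its confidence interval in SAP 9.1.1 would shift as well.

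The wording cannot be put down to loose drafting, because the same section separates strict from inclusive limits elsewhere, in the EULAR response table and in the remission rule. The amendment log in SAP 1.1 does not mark either ACR rule as superseded. The SAP synopsis wants all decisions on the final analyses made before database freeze, and this decision is still open in the text.

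**Working it through.** **Step 1. Reproduce the plan's own examples and see whether they decide the point.** Percent changes recomputed from the listed values:

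| Component | Example 1 | Example 2 |
|---|---|---|
| TJC68 | 43 to 14: -67.44 | 43 to 14: -67.44 |
| SJC66 | 38 to 44: +15.79 | 38 to 14: -63.16 |
| Pain | 46 to 20: -56.52 | 46 to 10: -78.26 |
| Patient global | 85 to 31: -63.53 | 85 to 31: -63.53 |
| Physician global | 75 to 27: -64.00 | 75 to 27: -64.00 |
| CRP | 2.8 to 2.0: -28.57 | 2.8 to 1.0: -64.29 |
| HAQ-DI | 11.6 to 7.2: -37.93 | 11.6 to 1.2: -89.66 |

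All 14 agree with the SAP to the nearest whole percent. Example 1 fails ACR20 under either sign. Example 2 meets ACR50 and fails ACR70 under either sign. The values closest to the cutoffs are -28.57 (to -20), -56.52 (to -50) and -67.44 (to -70). None is a tie, so the examples are silent on the sign.

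**Step 2. A case that separates the two rules.** Both joint counts go from 10 to 8: 100 × (8 − 10)/10 = -20.0%. Three other measures change by -30% and two do not change. Under the procedure text, -20 < -20 is false and the subject is a non-responder. Under the flowchart, -20 ≤ -20 is true, 3 of 5 are met and the subject is a responder. The same happens at the joint step for 10 to 5 (-50.0%) and 10 to 3 (-70.0%), if the strict sign is taken to apply to ACR50 and ACR70.

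**Step 3. Where ties can arise.** A baseline count n allows an exact fall of X% when n × X/100 is a whole number. The protocol requires at least 4 swollen and 4 tender joints (inclusion criterion 5). The documents give no distribution above that minimum; 24 is an upper limit chosen here for illustration.

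| Baseline | ACR20 | ACR50 | ACR70 |
|---|---|---|---|
| Joint count 4–24 (21 values) | 4 (5, 10, 15, 20) | 11 (every even count) | 2 (10, 20) |
| TJC68, 4–68 (65 values) | 13 | 33 | 6 |
| SJC66, 4–66 (63 values) | 13 | 32 | 6 |
| HAQ-DI, 8 areas scored (24 non-zero scores) | 4 | 12 | 2 |

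The HAQ-DI row matters at the 3-of-5 step. SAP 11.5.4 says: "The average of these non-missing functional area scores defines the continuous HAQ-DI score ranging from 0 to 3". With all 8 areas scored it moves in steps of 1/8 = 0.125, so for example 1.0 to 0.5 is exactly -50%.

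**Step 4. Effect of one tie.** With 10 subjects per arm, 1/10 = 10 percentage points on that arm's rate. A tie in a component that does not decide the response changes nothing.

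**The case against.** Four points can be made on the other side, and each limits the finding.

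- **The explicit contradiction covers ACR20 only.** A reader might infer that the SAP also contradicts itself outright on ACR50 and ACR70. It does not. For those levels the procedure text has no sign, and the only sign the SAP states is the flowchart's ≤ -X. Carrying the strict limit over is one reading; taking the sign from the flowchart is another. This stands: for ACR50 and ACR70 the fault is ambiguity.

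- **The protocol does not rule the strict sign out.** Its wording reads more naturally as including exactly 20%, but it names no sign. This stands too: only the flowchart directly supports ≤.

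- **The size cannot be estimated from the documents.** It is tempting to turn the tie counts into an expected loss of responders. Suppose baseline counts are uniform on 4 to 24 and each joint stays active with probability 0.2 to 0.5. The share passing the joint step under ≤ that fails under < is then 0.0–1.1% for ACR20 if tender and swollen counts are fully concordant, and 0.1–2.1% if they are independent. For ACR50 the figures are 1.7–21.5% and 3.3–38.4%. Every input is invented, and the top value needs the same 0.5 for every subject, which puts the mean outcome on the cutoff. Letting that probability vary between subjects (mean 0.5, SD 0.20–0.25, shared by both counts) cuts 38.4% to about 12–16%. All these figures stop before the 3-of-5 step, so none is a change in an ACR rate, and the ACR50 ones apply only if the strict sign carries over.

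- **The consequence is small.** The endpoints are exploratory, no hypothesis is tested, and Listing 46 shows the ACR components, so ties can be found afterwards. That lowers the severity. It does not remove the need for one rule, since finding ties after unblinding means choosing the sign with results in view.

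**Conclusion.** The point holds as a minor internal inconsistency. For ACR20, SAP 11.5.4 states two incompatible limits, and nothing else in the documents decides between them. For ACR50 and ACR70 the sign is unclear.

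The conclusion rests only on the wording and on the scales being discrete; it needs no assumption about the data. What can be said of size is which baselines allow a tie and that one reclassified subject is worth 10 points in a 10-subject arm. How many subjects would be reclassified is unknown and may be none. Nothing here touches the primary pharmacokinetic and safety analyses or the secondary DAS28(CRP) analysis.

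**What to change.** In the ACR procedure of SAP 11.5.4, before unblinding:

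- In the ACR20 bullet, replace *less than -20%* with *less than or equal to -20%* in both places.
- Replace the following bullet with: *ACR50 and ACR70 are calculated in the same way with ≤ -50% and ≤ -70%.*

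This brings the text into line with the flowchart, which needs no change, and both worked examples keep their verdicts. The cost is two bullets of SAP wording, with no change to data collection or to any primary or secondary analysis.

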## Flowchart

Calculate %change from baseline of a subject  
in 7 specific components of the ACR assessments

**7 components**

1. Tender/Painful Joint Count (68)
2. Swollen Joint Count (66)
3. Patient's Assessment of Arthritis Pain
4. Patient's Global Assessment of Arthritis
5. Physician's Global Assessment of Arthritis
6. CRP
7. Health Assessment Questionnaire-Disability Index (HAQ-DI)

%changes from baseline in **tender and swollen joint count**  $\leq -X$

Yes

No

The subject did not meet the criteria for ACRX

%changes from baseline in 3 of the **5 remaining components**  $\leq -X$

Yes

No

The subject did not meet the criteria for ACRX

The subject met the criteria for ACRX

**Examples**

- The subject did not met the criteria for ACR20

Component	Baseline	Post-dose visit value	%change
TJC68	43	14	-67
SJC66	38	44	16
Patient's Assessment of Arthritis Pain	46	20	-57
Patient's Global Assessment of Arthritis	85	31	-64
Physician's Global Assessment of Arthritis	75	27	-64
CRP	2.8	2.0	-29
HAQ-DI	11.6	7.2	-38

- The subject met the criteria for ACR50 but not ACR70

Component	Baseline	Post-dose visit value	%change
TJC68	43	14	-67
SJC66	38	14	-63
Patient's Assessment of Arthritis Pain	46	10	-78
Patient's Global Assessment of Arthritis	85	31	-64
Physician's Global Assessment of Arthritis	75	27	-64
CRP	2.8	1.0	-64
HAQ-DI	11.6	1.2	-90

**Disease Activity Score**[Prevoo, 1995; Fransen, 2005; Wells, 2009]

- The DAS assessment is a derived measurement with differential weighting given to each component. The DAS28 (CRP) and DAS28 (ESR) will be calculated at each assessment time point.
- The components of the DAS28 arthritis assessment include:
  - Tender Joint Count 28 (TJC28)
  - Swollen Joint Count 28 (SJC28)
  - C-reactive protein (CRP) (in mg/L) or Erythrocyte sedimentation rate (ESR) (in mm/hr)
  - Patient's Global Assessment of Arthritis (PtGA) (visual analogue scale with values from 0 = best to 100 = worst)

**DAS28 (CRP)**

- The DAS28 (CRP) will be calculated using the following formula:

$$DAS28(CRP) = 0.56 \times \sqrt{TJC28} + 0.28 \times \sqrt{SJC28} + 0.36 \times \ln(CRP + 1) + 0.014 \times PtGA + 0.96$$

- If one of the components is missing at an individual assessment point, the DAS28 (CRP) value for that assessment will be set to missing

### DAS28 (ESR)

- The DAS28 (ESR) will be calculated using the following formula:

$$DAS28(ESR) = 0.56 \times \sqrt{TJC28} + 0.28 \times \sqrt{SJC28} + 0.70 \times \ln(ESR) + 0.014 \times PtGA$$

- If one of the components is missing at an individual assessment point, the DAS28 (ESR) value for that assessment will be set to missing. An ESR value of 0 will be substituted with ESR = 1 for the calculation of DAS28 (ESR).

